6.0 STUDY PLAN

6.1 SUMMARY OF STUDY PLAN

Pre-adolescent and AYA patients with newly diagnosed HR-ALL will have dietary and activity preferences assessed by a registered dietician (RD) and physical therapist (PT) at the start of induction.

Subjects will receive an individualized comprehensive dietary and physical activity plan. The RD and PT will devise a personalized dietary and activity intervention aimed at creating a minimum 10% caloric deficit each day (10% nutritional + exercise) throughout the four weeks of induction therapy. Adherence to the intervention will be assessed by the RD and PT at regular weekly intervals at routine clinic visits for chemotherapy and with home phone-calls between clinic visits. Home and hospital activity will also be recorded using a wearable electronic movement monitoring device (Fitbit ®) for all participants. A list of representative “menu” of possible activity interventions from which subjects may choose is provided as a separate Appendix. The primary efficacy of the intervention will be assessed in comparison to a recent historical control via determining the change in body fat percentage (and lean muscle) during induction as quantified by dual-energy x-ray absorptiometry (DXA). A key secondary aim will be the effectiveness of the intervention to reduce chemoresistance as evidenced by decreased prevalence of leukemia minimal residual disease (MRD) at the end of induction. MRD using multicolor flow cytometry is routinely assessed as a predictor of outcome in all patients with HR-ALL. Exploratory analyses will also examine biomarkers of the proposed mechanism including adiposity and intervention-related changes in leukemogenic signaling pathways, oxidative stress, and cellular metabolism. Parent- and subject-reported QOL assessments will consist of the PedsQL and Child and Adolescent Scale of Participation (CASP) surveys (see separate Appendix) and will be conducted pre- and post-induction and at two delayed time-points (mid-point of intensive chemotherapy [3 months from diagnosis] and at end of intensive chemotherapy phase [10 months from diagnosis] to assess the psychosocial benefits of the intervention.

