13.0 STATISTICAL CONSIDERATIONS AND EVALUATION CRITERIA

13.1 SAMPLE SIZE AND STUDY DURATION

Based on available data over a recent 3-year period (2012-2014), we predict at least 43-45 subjects ≥ 10 years of age with HR-ALL patients will be eligible for enrollment during the three year study. We anticipate $>85\%$ of subjects to be enrolled & evaluable for the primary and secondary aim surrounding the Day 29 time-point, for an effective sample size of at least 36 subjects. As of AMD03, additional site(s) were added to gain experience with the study intervention at outside institutions; there is no change to the target study accrual goal of 36 evaluable subjects.

As subjects historically gain body fat during induction irrespective of starting body composition (i.e. both those lean and those overweight/obese gain body fat), we will enroll a goal of 18 overweight/obese and 18 lean subjects on the study to evaluate for an overall effect of the intervention, as well as a differential effect in those “lean” by BMI percentile. We will continuously monitor accrual by weight category with a minimum final target accrual of 14 overweight/obese and 22 lean subjects (40/60) which, as below, preserves our ability to detect an effect on body fat and on the key secondary aim of MRD. For assessment of the delayed endpoints, we expect that 80% of the initial cohort will additionally be evaluable for secondary the aims at the final pre-start of maintenance time-point (due to treatment-related morbidity/mortality/lost-to-follow-up).

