13.4 EXPLORATORY ENDPOINTS EVALUATION

To evaluate persistence or extinguishing of this effect during continued dose-intensive phases of chemotherapy

Reported continued adherence to activity and dietary recommendations will be evaluated by the RD and PT as per last prescribed or recommended from the intervention versus actual minutes/dietary intake at the delayed time-points of start of Interim Maintenance ($\sim +3$ months) and start of Maintenance ($\sim +10$ months). Activity and dietary intake patterns will also be compared to baseline at-diagnosis levels. Similar exploratory analysis will examine the effect of age, sex, race, and/or ethnicity.

To characterize the direct impact as compared to baseline of the intervention on self- and family- reported quality of life (QOL) outcomes including fatigue, mood, social interaction, and cognitive impairment reported via the PedsQL questionnaire and Child and Adolescent Scale of Participation (CASP) following the induction phase and serially during dose-intensive phases of chemotherapy

The PedsQL questionnaire returns a QOL score between 0-100 for each patient at each time-point. The CASP is scored as a percentage and then normalized to a 100 point score. Differences during therapy will be compared using a two-sided, paired t-test during induction (the intervention) and using repeated measures analysis for all four time-points.

To quantify the effect of adiposity at diagnosis on the activity of leukemogenic JAK2/STAT3, PIK3K/AKT/mTOR, MAPK/ERK, and other signaling pathways in leukemia cells as determined by kinase phosphorylation

Differences in levels of expression of the pathways will be analyzed according to body fat percentage (adiposity) using a two-sided, two-sample t-test for the different pathways as well visually for overall trends in related pathways.

To quantify the effect of adiposity and of the intervention on the metabolic activity of leukemia blasts and of adipocytes as assessed by IGF-1, other obesity-associated cytokine signaling pathways, adiponectin, leptin, free fatty acid synthesis and metabolism, and levels oxidative stress.

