Exploratory analyses using similar t-tests will be performed to explore the effects of adiposity at diagnosis on adipokines, obesity-associated cytokines, oxidative stress, and measures of cellular metabolism. The effect of the intervention on oxidative stress and free fatty acid synthesis will be analyzed using paired t-tests for pre/post intervention and compared to samples from the historical cohort.

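### Section 13.4 tests the effect of adiposity at diagnosis with two-sample t-tests on a continuous body-fat measure and states no cut; a regression slope should lead, with one pre-stated group comparison as support

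*Combined protocol and SAP*

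**What the plan says.** Section 13.4 restates the third exploratory aim as "To quantify the effect of adiposity at diagnosis on the activity of leukemogenic JAK2/STAT3" and other pathways. The levels are to be "analyzed according to body fat percentage (adiposity) using a two-sided, two-sample t-test for the different pathways", together with a visual look at trends across related pathways. For the metabolic aim it adds: "Exploratory analyses using similar t-tests will be performed to explore the effects of adiposity at diagnosis" on adipokines, cytokines, oxidative stress and cellular metabolism. The effect of the intervention on oxidative stress and fatty acid synthesis is handled separately, by paired pre/post tests and a comparison with historical samples.

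Body fat percentage is the DXA measure (Sections 6.1 and 13.2). No section divides it into groups.

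The only two-group structure is in Section 13.1: "we will enroll a goal of 18 overweight/obese and 18 lean subjects on the study", with a minimum final accrual of 14 overweight/obese and 22 lean. That section describes lean status by BMI percentile. Section 13.3 uses the overweight/obese subset for MRD. Section 13.4 does not mention these groups.

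**The concern.** Two analysts working from Section 13.4 could not be sure of running the same test. One might split at the body-fat median, another at a clinical body-fat threshold, and a third might use the BMI groups. The result for a given marker can depend on that choice.

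The method also fits the aim poorly. The aim is to quantify an effect of adiposity. A slope with a confidence interval does that, whereas a difference between two undefined groups does not. If markers change steadily with body fat, splitting also loses power in a small study. The target is 36 subjects evaluable at Day 29. Baseline serum analyses might include somewhat more, since they need only the diagnosis scan and sample. Leukaemia-cell assays will probably have fewer: the Section 9.1 footnotes restrict blood blasts to subjects with an absolute count of at least 500/µL, and research marrow to cases with enough specimen.

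**Working it through.** Section 13.4 gives no sample size, power or alpha for these analyses, so there is no stated figure to reproduce.

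**Inputs from the protocol.** 36 evaluable subjects; weight groups of 18/18, or 14/22 at the minimum (Section 13.1); body fat at diagnosis 23.3 ± 9.1% in the earlier cohort (Section 3.0); two-sided tests (Section 13.4).

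**Assumed.** A 5% level, which the protocol states only for the primary endpoint; a linear relation; a range of correlations between body fat and marker; and 24 samples as an illustration for the cell assays. The documents give no shape, correlation or assay count.

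**Information kept by a split.** For normally distributed body fat, cutting so that a proportion p lies on one side keeps φ(z_p)² / [p(1−p)] of the information in the slope.
- Median: 0.3989² / 0.25 = 0.637, so 36 × 0.637 ≈ 23 subjects' worth.
- 14:22 (p = 0.389): 0.618, so 36 × 0.618 ≈ 22.
- Gamma distribution matched to 23.3 ± 9.1 (shape (23.3/9.1)² = 6.56): 0.610 and 0.638.
- Two equal normal groups 2 SD apart: 0.680 and 0.654.

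The loss therefore runs from 32% to 39%.

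**Power under a linear effect.** Simulation with 40,000 samples per setting and bivariate normal data, comparing the slope t-test with a pooled t-test after ranking on body fat. The second split is 14:22 at n = 36 and 9:15 at n = 24.

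| n | Correlation | Slope | Median split | 14:22 or 9:15 split |
|---|---|---|---|---|
| 36 | 0.30 | 44% | 29% | 28% |
| 36 | 0.40 | 69% | 48% | 47% |
| 36 | 0.45 | 81% | 59% | 58% |
| 24 | 0.30 | 30% | 20% | 19% |
| 24 | 0.40 | 51% | 33% | 32% |
| 24 | 0.45 | 62% | 41% | 40% |

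For scale, a correlation of 0.40 is 0.40 × 10/9.1 = 0.44 marker SD per 10 points of body fat. Its 95% half-width at n = 36 is about 2.03 × √(1 − 0.16)/√34 × 10/9.1 ≈ 0.35.

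**Dependence on the cut.** At n = 36 and correlations of 0.30, 0.40 and 0.45, the median and 14:22 splits disagree on significance in 19%, 22% and 21% of trials. As a benchmark, Pearson and Spearman tests on the same data disagree in 10–12%.

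**If the BMI groups are used.** Suppose markers follow body fat with correlation 0.40. For an assumed BMI–body fat correlation of 0.7, 0.8 or 0.9, the 18/18 BMI comparison has 26%, 33% or 40% power, against 48% for a body-fat median split.

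**Cases that favour the split.**
- Bimodal body fat from 18/18 enrolment: at correlation 0.40 the slope's lead over the median split falls from 21 points to about 18, 15 and 10 when the groups are 2, 3 and 4 SD apart.
- A true step of 1 SD at the median: correct split 83%, slope 61%, 14:22 split 61%.
- A true step above which 14 subjects lie: correct split 81%, slope 57%, median split 59%.

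**The case against.** The strongest reply is that the only omission is the group definition, and one clause would repair it. On that view, putting the slope first is a preference, which wins under a linear effect and loses under a step. Section 3.0 reports that MRD positivity rose from the overweight range upward, which looks more like a threshold than a line. The Section 13.1 groups also serve analysis as well as recruitment, so they are a natural reading of a two-sample test, and the visual look at trends shows a descriptive purpose.

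Much of this stands. The power gain depends on a shape that the documents do not give. The Section 3.0 finding concerns BMI and MRD, not these markers, and the same section analysed BMI percentile as continuous, so it does not settle the shape. The Section 13.1 groups are a plausible intention, but Section 13.4 names body fat percentage and does not point to them. No numeric lean/overweight boundary is given either; Section 5.2 defines only the underweight end. The step case supports a split only when its cut is right, and none is stated.

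A reader might go further and infer that cuts will be chosen after seeing results, inflating false positives. With no true effect, taking the best of four plausible cuts would raise the per-marker rate from 5% to about 12%. Nothing in the documents suggests such a search is intended; the text merely does not rule it out.

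**Conclusion.** The gap is real: Section 13.4 specifies a two-group test on a continuous measure without defining the groups. That conclusion needs no assumption. The efficiency argument is conditional. With a roughly linear relation, splitting costs about a third or more of the information, or about 21 points of power at n = 36 and correlation 0.40. The cost shrinks if enrolment makes body fat strongly bimodal, and it reverses for a step at the correct cut. The slope is still the better lead analysis, because it answers the stated aim and needs no cut.

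A reader might infer that the trial's main conclusions are weakened. The documents do not support that: these are exploratory aims without power claims, and the primary endpoint, MRD and the paired pre/post comparisons do not use this analysis. Nor is 36 a ceiling, since Section 13.1 says at least that many. This is a minor improvement.

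**What to change.** In Section 13.4, replace the two-sample t-tests for adiposity at diagnosis as follows.

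1. **Main analysis:** linear regression of each marker on continuous DXA body fat percentage at diagnosis. Include age and sex as covariates where the number of samples allows, since the study pools both sexes and ages 10 to 21. Report the slope per 10 percentage points with a 95% CI and a scatterplot. List in advance which markers are log-transformed.
2. **Supporting analysis:** one group comparison, labelled as supporting, with its grouping stated in advance. This could be the body-fat median, or the Section 13.1 groups described as BMI groups with their boundary given.

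If the t-test is kept as the main analysis, the minimum change is to state that one grouping.

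The cost is wording and slightly more analysis work; no new data are needed. The main test would have less power if the true effect is a step at the chosen cut. A quadratic term would not reliably reveal one: it is significant in about 6% of simulated trials for a median step and 8% for the step with 14 subjects above it. That is the reason to keep the group comparison. It must not count as a second route to a positive result, because accepting either test raises the 5% false-positive rate to about 7.5%.

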14.0 ADVERSE EVENT REPORTING REQUIREMENTS

Adverse event (AE) data collection and reporting are required as part of every clinical trial to ensure the safety of patients enrolled in the studies as well as those who will enroll in future studies using similar agents. Adverse events are reported in a prescribed manner at scheduled times during the trial.

Induction chemotherapy has many associated toxicities due to the intensity of regimen, and these will be monitored per routine care by the treatment team and/or by the appropriate research team if the subject is enrolled on a concurrent therapeutic research study.

We will not record non-targeted toxicities (those described in clinical history Section 9.1) due to the underlying leukemia or treatment regimen.

As this trial consists of behavioral interventions (diet and exercise) that are within the scope of standard of care for patients, we will ONLY collect AE's that occur *during* or *immediately following* the exercise activities. If this should occur, the AE will be reported to the local IRB and the coordinating IRB (CHLA).

For an AE that occurs as above, we will record and report using the National Cancer Institute Common Terminology Criteria for Adverse Events v4.0 (CTCAE) available for download at <http://ctep.cancer.gov>.

All reporting of adverse events must include:

- severity (grade) of the event
- duration of the event
- attribution to the study (i.e. how the event is related to the study).
- whether hospitalization was necessary (or prolonged) for subjects

Categories of attribution in order of increasing likelihood are:

- Unrelated
- Unlikely
- Possible
- Probable
- Definite

All adverse events will be labeled "unexpected" for this behavioral study intervention.

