9.3 BONE MARROW ASPIRATE & BIOPSY

As per the preceding CHLA ALL Obesity Environment & Microenvironment Study #2, subjects on study may require extra bone marrow aspirate and biopsy for study purposes. The bone marrow aspirates will be collected during the same anesthesia and procedure being done for clinical care purposes and will be collected after the clinical specimen is obtained. If there is insufficient specimen available, there will be no additional aspirates (needle punctures) performed for study purposes only and no bone marrow leukemia cells will be expected from that time-point for study. If a routine bone marrow biopsy at diagnosis was performed with sufficient extra specimen, a piece will be collected for study purposes. Subjects undergoing bone marrow aspiration at end of induction for clinical purposes will also require a single additional research-only bone marrow biopsy to be performed at the same time. For sites that do not (or cannot) collect bone marrow biopsies in saline, marrow biopsies will not be collected for this study.

Similarly, bone marrow biopsies not collected in saline (for any reason) will not be obtained for this study as it precludes analysis of the marrow fat.

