11.2 BONE MARROW ASPIRATE & BIOPSY

All research procedures will be coordinated with clinical bone marrow aspirates and biopsies. If there is insufficient specimen available from the bone marrow aspirate, there will be no additional aspirates performed for study purposes only. As such, there is minimal additional risk to this procedure. The research-only biopsy at the end of induction will be coordinated with the routine bone marrow aspirate; the biopsy will be obtained per standard practice using the same skin puncture with minimal prolongation of anesthesia (typically less than 3 minutes) with minimal additional post-operative discomfort due to the addition of the biopsy to the aspirate. Post-operative care routinely includes assessments of discomfort and the clinical care teams will assist in managing this as needed.

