14.1 EXPEDITED REPORTING OF ADVERSE EVENTS

As a behavioral intervention that does not pose more than minimal risk to the subject, expedited reporting will only be required in the case:

Toxicities that occur during this protocol-specified activity (as described above) and cause or prolong hospitalization will be reported in an expedited manner to the IRB within 5 business days.

Toxicities that are \geq Grade 4 and occur during the protocol-specified activity (as described above) will be reported in an expedited manner to the IRB within 5 business days.

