16.0 DATA AND SAFETY MONITORING PLAN

The Principal Investigators or designees will be available to answer questions of patients on the research protocol. As the study intervention constitutes a standard-of-care behavioral intervention only, data and safety monitoring for all patients enrolled on the study will be conducted by the study committee on an ongoing basis while the study is open.

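### Adverse-event collection and expedited reporting are limited to exercise, so the protocol states no rule for complications of its research-only marrow biopsy or of study venipuncture

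*Combined protocol and SAP*

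**What the plan says.** **Collection (Section 14.0).** The scope is set in one sentence: "we will ONLY collect AE's that occur *during* or *immediately following* the exercise activities". Those events are the ones sent to the local and coordinating IRBs. The reason comes in the same sentence: "As this trial consists of behavioral interventions (diet and exercise) that are within the scope of standard of care for patients".

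**Expedited reporting (Section 14.1).** The section opens "As a behavioral intervention that does not pose more than minimal risk to the subject, expedited reporting will only be required in the case" and then gives two triggers. The hospitalization trigger reads "Toxicities that occur during this protocol-specified activity (as described above) and cause or prolong hospitalization will be reported in an expedited manner". The trigger for Grade 4 or higher covers toxicities that "occur during the protocol-specified activity (as described above) will be reported in an expedited manner to the IRB within 5 business days". In both, the activity described above is the exercise of Section 14.0.

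**Research procedures (Sections 9.1, 9.3, 11.1, 11.2).** Section 9.3 states: "Subjects undergoing bone marrow aspiration at end of induction for clinical purposes will also require a single additional research-only bone marrow biopsy". It exempts sites that do not or cannot collect biopsies in saline. In the Section 9.1 schedule the diagnosis biopsy carries the standard-of-care asterisk and the end-of-induction biopsy does not. Section 11.2 describes the added burden of the biopsy as "minimal prolongation of anesthesia (typically less than 3 minutes) with minimal additional post-operative discomfort" and leaves discomfort to the clinical teams. Section 11.1 says subjects without central lines will need venipuncture, combined with clinical draws where possible. It names pain, bruising, faintness and, very rarely, infection as risks.

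**The concern.** The narrow scope rests on a description of the trial as diet and exercise. That description leaves out an invasive procedure which the same protocol requires and labels as research-only. Section 14.0 itself begins from the position that every trial must collect and report adverse events to protect its patients.

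At stake is safety information on procedures done solely for research, in a population that is largely minors. A site that follows Section 14 to the letter would not record biopsy-site bleeding, infection, marked pain or an anesthesia event as an adverse event, because none of these occurs during or just after exercise. If the final report then said there were no study-related adverse events, that statement would partly reflect the collection rule and not only what happened to patients. Sites were added by amendment, so the written rule needs to be clear to teams that did not write it.

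**Working it through.** There is no figure to reproduce and no arithmetic to do. The check is whether any section would capture a complication of a research procedure. Take a biopsy-site bleed after the end-of-induction procedure that is Grade 4 and lengthens the hospital stay, and follow it through the text.

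1. **Is the procedure research or care?** Section 9.3 calls it research-only, and the Section 9.1 schedule agrees by leaving off the standard-of-care asterisk. The bleed is therefore not simply a consequence of routine treatment.

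2. **Does Section 14.0 exclude it as a treatment toxicity?** No. The sentences on routine monitoring of induction toxicity, and on not recording certain toxicities, concern the chemotherapy regimen and the underlying leukemia. A research biopsy is neither. What excludes the bleed is the sentence limiting collection to exercise.

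3. **Does Section 14.1 bring it back?** No. Both triggers would be met on severity (a lengthened stay; Grade 4), but both also require the event to occur during the exercise activity. The bleed fails that condition in each sentence separately.

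4. **Does the clinical history bring it back?** Only in part. The Section 9.1 footnote lists, among other items, surgeries, ICU admissions, Grade 3 or 4 hepatic or pancreatic toxicity, osteonecrosis and fracture. Procedure-site bleeding, infection, pain and anesthesia events are not named. If the bleed led to an ICU admission or an operation, that consequence would be recorded, without attribution to the biopsy and without an IRB step.

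5. **Does Section 11.2 bring it back?** No. It assigns post-operative discomfort to the clinical teams, which is management and not research recording.

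6. **Does Section 16.0 bring it back?** No. It provides ongoing monitoring by the study committee but states no rule on procedure events, and under Section 14.0 no such adverse events would be collected for it.

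The same path applies to a complication of venipuncture done only for the study. The Section 9.1 schedule places the lipid panel and research laboratory samples at four time-points: diagnosis, end of induction, start of interim maintenance and start of maintenance. Any of these could involve a study-only needle-stick in a subject without a central line.

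**The case against.** The strongest reply is that the gap is small and partly covered elsewhere. The biopsy uses the clinical aspirate's skin puncture and anesthesia, adds typically under three minutes, and is followed by routine post-operative care. The gravest complications could appear in the clinical history, and the later history at the start of interim maintenance could pick them up in retrospect. Biopsy safety is not an aim, and no endpoint depends on it. All of this stands and limits the priority of the point. It does not supply a rule for recording, attributing or reporting. The shared puncture makes attribution harder, but the graded attribution categories already in Section 14.0 exist for such cases.

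Four stronger readings are tempting and are not supported:

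- **That the IRBs could not learn of a biopsy complication.** Each site works under local IRB approval, and site or IRB policy may require such reports. Those policies are not in the documents. What can be said is that the protocol states no route.
- **That Section 11.2's statement of minimal added risk becomes uncheckable.** That sentence directly follows the text on aspirates. For the biopsy, the section speaks only of anesthesia time and discomfort.
- **That the biopsy is universal, or the only research invasive procedure.** It depends on a clinical aspirate and on saline collection, and study venipuncture may also occur. An upper limit on the complication rate based on 36 subjects would not be justified either: 36 is the accrual target for evaluable subjects, not a count of biopsies.
- **That Section 16.0 is wrong.** Its phrase, "As the study intervention constitutes a standard-of-care behavioral intervention only", describes the intervention, which is behavioral. The biopsy is a study assessment.

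**Conclusion.** The point holds as a mismatch of scope. Section 14 states an explicit, exclusive rule built on exercise, while Sections 9.3 and 11.1 provide for invasive research procedures outside it. Followed literally, the rule leaves every complication of those procedures outside adverse-event collection, attribution and protocol-stated reporting, whatever its grade.

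The number of subjects affected cannot be given: the documents do not say how many will have a clinical end-of-induction aspirate at a saline-collecting site, or how many will lack a central line. The body-fat and MRD analyses are untouched. The conclusion assumes that sites apply Section 14 as written and that the front matter and consent documents, which were not available, contain no rule that fills the gap. It should be corrected because the correction is cheap and concerns patient safety, not because the described risk is large.

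**What to change.** 1. **Section 14.0:** extend collection to events possibly related to research-only procedures, meaning the end-of-induction research biopsy and study-only venipuncture, from the procedure to the next routine clinic visit. Use the CTCAE grading and attribution categories already specified, and the same reporting to the local and coordinating IRBs.
2. **Section 14.1:** extend both trigger sentences, the one on hospitalization and the one on Grade 4 or higher, to events during or following a research-only procedure. The two are worded slightly differently, so changing only one would leave the other limited to exercise.
3. **Rationale in Sections 14.0 and 14.1:** acknowledge the research biopsy alongside the behavioral intervention. Section 16.0 needs no change on this account.

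**Cost.** Protocol wording and a short added CRF entry. This is some new collection: after Day 29 the next scheduled study time-point is the start of interim maintenance, so the entry would be completed from the next routine clinic visit. Expect a few more low-grade events such as pain or bruising, and some uncertainty in attributing events between the research biopsy and the clinical aspirate. Treatment, endpoints and sample size are unchanged.
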